***Immunogenicity Analysis:***

The vaccine immunogenicity was determined by the presence and quantity of functional Chikungunya virus neutralizing antibodies in the sera of vaccinated subjects. The neutralization titers were determined by 50% plaque reduction neutralization test (PRNT50) and total antibody levels were determined by hemagglutination inhibition assays (HIA).

The primary end-point of the study, which was immunogenicity on day 28 after the first vaccination, showed that a single MV-CHIK immunization elicits functional antibodies in all treatment cohorts. The medium and high dose groups induced similar levels of neutralizing antibodies, which were significantly higher than the low dose group and the Priorix control groups. A second immunization at one or three months interval boosted the titers in all treatment groups clearly, figure 2). The low dose group showed relatively low titers of both functional and total antibody levels. A second immunization did boost the titers clearly, however, this dose level is not suitable for a single shot vaccine. The medium dose group elicited significantly higher titers after one or two immunizations. The highest functional and total anti-CHIKV titers were elicited in the highest dose group. The functional antibodies were persistent over the study period. Very similar results were obtained by HAI. Total antibody levels have been induced by a single immunization, and boosted by a second dose.

The Measles antibody titers as measured by ELISA were boosted in all treatment groups (MV-CHIK and Priorix®) after the first vaccination. No clear trend between the individual groups was visible but an increase in Measles virus dose increased the geometric mean titer (GMT). The measles ELISA titers that were induced after the first immunization were close to the detection limit of the assay. Therefore, a not additive effect was visible after a second immunization.

The subjects that entered the study were not pre-selected for a specifically high or low Measles antibody titer. The subjects were randomly allocated to the individual treatment cohorts. To analyze the effect of pre-existing anti-measles immunity on the immunogenicity of the MV-CHIK vaccine, we investigated if a baseline anti-measles titer would cause a difference between the PRNT50 titers on day 28 after the first immunization of all subjects in MV-CHIK dose groups (independently of their dose group). This analysis showed that subjects that had a low, medium or high measles titer at baseline were equally prone for the immunogenicity of the MV-CHIK vaccine. Thus, the pre-existing immunity to the vaccine vector did not interfere with the vaccine immunogenicity.

[figure not shown]

Figure 2: Induction of neutralizing antibodies after two immunizations – 1 month interval (Upper panel), 3 month interval (Lower panel). The data are depicted as 50% plaque reduction neutralization titers (PRNT50) for the individual subjects and Geometric Mean titers (GMT) for the cohorts on day 0, 28 and 56 (upper panel) or day 120 (lower panel). The cohorts were divided in three dose groups: low ( $1.5 \times 10^4$  TCID50/mL) medium ( $7.5 \times 10^4$  TCID50/mL) and high ( $3 \times 10^5$  TCID50/mL); the control group received Priorix, a commercially available Measles, mumps rubella vaccine. Titers <10 are referred as seronegative samples. For the purpose of display in the graph and for calculation of a GMT the negative values were depicted as 5.

### **Safety Analysis:**

Vital sign checks including measurement of blood pressure, pulse rate and axillary body temperature as well as physical examination were performed at all visits. Additionally, the injection site was inspected and evaluated for local side effects by the investigator at each visit and before and 6 hours after each vaccination. Grading of local pain, tenderness, redness, swelling, itching and induration was performed according to the respective FDA guidance for industry and the guidance of the Brighton Collaboration. Accordingly, local side effects were graded as mild (grade 1), moderate (grade 2), severe (grade 3) and potentially life-threatening

(grade 4). All participants were provided with a template that allows estimation of local reactions (supplementary information).

Pain, itching and induration were graded as mild if they did not interfere with daily activity, as moderate if they did compromise activity or necessitated repeated use of non-narcotic pain reliever/anti-inflammatory and pain relieving ointment (itching and induration) and as severe if they prevented daily activity. Grade 4 pain/itching included the need for Emergency room (ER) visit or hospitalization. Swelling and erythema below a diameter of 5 cm were rated as mild. Swelling/erythema exceeding 10 cm in diameter were considered to be severe and necrosis indicated grade 4 swelling/erythema (supplementary information).

Furthermore, participants were requested to keep a study diary in order to record all local and systemic symptoms and any adverse event occurring during the first two weeks after vaccination starting with the first entry 6 hours ( $\pm 1$ ) after vaccination. The subjects themselves recorded the assessments once daily at the same time each day. Completeness and accuracy of self-reported symptoms and side effects were verified at each visit by a study-related physician. Diaries were reviewed together with the particular participant at each visit and participants were interviewed for any adverse events. Diaries had to be signed by both the particular participant and the reviewing physician at the end of each vaccination period to confirm and ensure completeness and reliability of self-reporting. The investigator collected the diaries at each visit and new ones were dispensed after vaccination.

Solicited and non-solicited adverse events (AEs) were reported separately. Solicited AEs included pyrexia, flu like illness, headache and injection-site- related side effects (erythema, swelling, induration and pain).

In general, MV-CHIK vaccine had an acceptable tolerability profile. All adverse events observed were treatment emergent AEs and were recovered without any sequelae before or at study end.

The most frequently solicited AEs were headache (57.1%), injection side pain (50.0%), influenza like illness (45.2%), vaccination side pain (40.5%), fatigue (38.1%), nausea (31.0%), myalgia (26.2%) and arthralgia (23.8%). The most frequently related solicited AEs were injection side pain (50.0%), vaccination site pain (40.5%), headache (28.6%) and fatigue (23.8%).

Unsolicited AEs were AEs with none of the preferred terms of solicited AEs. 28 subjects (66.7%) had a total of 73 unsolicited AEs. Two subjects (4.8%) had two severe unsolicited AEs, five subjects (11.9%) had seven related unsolicited AEs and 19 subjects (45.2%) reported 33 unsolicited AEs where an action was taken. Two subjects (4.8%) reported two serious unsolicited AEs. The most frequently unsolicited AEs were nasopharyngitis (26.2%) and oropharyngeal pain (11.9%).

Special attention was directed to any occurrence of joint pain during the MV-CHIK study due to significant joint pathology caused by CHIKV. The subjects were asked to report any symptoms of joint pain in their subject diary and they were asked for any symptoms during each visit. Overall, 23.8% (10/42) of the subjects reported any signs of joint pain or arthralgia during the treatment period, 11.9% (5/42) of which were rated as related to the study treatment. In all 5 cases the joint pain was described as transient musculoskeletal pain, which was accompanied by flu like symptoms. Pain in the limbs associated with MV-CHIK injection was largely graded as mild (82%), was self-limiting and did not engender any withdrawals from the study. The rate of musculoskeletal pain decreased from 12% (n=5; 67% mild) at the first visit to 2% (n=1; 100% mild) at visit 5. No signs of inflammation were observed.

Severe and serious AEs occurred only for subjects treated with MV-CHIK. All serious AEs reported were non-local and unsolicited. Overall, seven severe AEs occurred (in six participants), of which five were solicited and related to vaccination including headache, local erythema, local induration, local pain and pyrexia.

The number of overall AEs and related AEs increased with the MV-CHIK dose. In addition, local reactions to MV-CHIK vaccination increased dose-dependently and were deemed related to the high inoculation volume (1mL) together with the formulation's salt buffer content.

The evaluation of safety laboratory parameters (hematology, serum chemistry, urinalysis) did not indicate any safety issues. There were no clinically relevant abnormalities observed in hematology, clinical chemistry, coagulation or urinalysis laboratory parameters.

The Clinical Study Report has been finalized in Q4/2014. The study results were published in Ramsauer et. al. Lancet Infect Dis 2015.

## 2.5 Study rationale

This Phase 2 trial is designed to investigate the immunogenicity, safety and tolerability of MV-CHIK.

Two different doses of MV-CHIK at a concentration of  $5 \times 10^4$  ( $\pm 0.5$  log) TCID50/dose and  $5 \times 10^5$  ( $\pm 0.5$  log) TCID50/dose per 0.3 mL will be assessed to healthy adults for the induction of functional anti-chikungunya neutralizing antibodies. In addition, the direct effect of the pre-existing vector immunity will be addressed by the immunization of a small subset of subjects with Priorix® prior immunization with two doses of MV-CHIK.

This study was designed according to the Note for Guidance on Clinical Evaluation of New Vaccines (CHMP/VWP/164653/2005), where applicable.

## 2.6 Benefit/Risk Assessment

The measles virus vector is well known. Possible risks that are frequently associated with vaccination are the occurrence of local reactions e.g. edema, induration and erythema, transient local pain or tenderness at the injection site as well as mild to moderate headache, myalgia, flu-like symptoms or fatigue.

In the past, a live virus vaccine against Chikungunya virus, which was based on an attenuated Chikungunya strain caused mild, transient arthralgia in immunized patients. The MV-CHIK vaccine is based on the measles virus technology and NO LIVE ATTENUATED Chikungunya virus is used. Thus, induction of Chikungunya like symptoms is not expected. However, the subjects will be monitored for occurrence of arthralgia.

As any other vaccine, MV-CHIK might induce allergic and anaphylactic reactions, apart from the described local reactions at the vaccination site and systemic flu-like reactions. In rare cases the injection can lead to a vasovagal reaction immediately after injection of the vaccine. The needle pricks for blood sampling may also cause local reactions such as edema. The subjects cannot expect direct benefit from study participation, except for potential boosting of measles immunity and mounting immunity to CHIKV.

If the clinical development of MV-CHIK is successful, this vaccine might help people, who are at risk of acquiring a possible life-threatening infection with CHIKV.

Thus, the benefit risk ratio is considered positive.

## 3 STUDY OBJECTIVES

### 3.1 Primary Objective

- To investigate the immunogenicity and safety of MV-CHIK 28 days after primary immunization regimen, comprising one or two vaccinations

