## 4 STUDY PLAN

### 4.1 Study Endpoints

#### 4.1.1 Primary endpoint

- Immunogenicity on day 56 confirmed by the presence of functional anti-chikungunya antibodies as determined by the plaque reduction neutralization test (PRNT50)

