## **11.2 Post vaccination reactogenicity assessments**

Please also refer to Table 2 and section 8.2 for exact time points.

All subjects enrolled in the study and who receive at least one immunization (Priorix® or MV-CHIK) will be followed up for at least 28 days after the last immunization.

Adverse event rates will be used to evaluate the secondary study objective.

Serious adverse events: see below for detailed clarification

Medically attended adverse events: All adverse events, for which the subjects were seeking medical care (i.e. doctor's office, emergency service, hospital, but not use of self-medication).

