## 13 STATISTICAL METHODS AND SAMPLE SIZE

The data will be analyzed by Assign Data Management and Biostatistics GmbH. A Statistical Analysis Plan (SAP) will be provided before database snapshot/closure describing in more detail how the study results will be evaluated.

A preliminary analysis including safety and immunogenicity data will be performed after all subjects completed Visit 3 (day 56). The goal of this analysis is to provide highly valuable data of the novel Chikungunya vaccine for further development. Results from this analysis will have no impact on the study design and treatment of the subjects in this study. A final analysis will be conducted once the last subject has completed the study.

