2.2 Conduct of Analysis

2.2.1 Preliminary Analysis

A preliminary analysis including safety and immunogenicity data will be performed in August 2017. The analysis was initially planned to be conducted after all subjects completed Visit 3 (Day 56) but was re-scheduled due to unforeseen delays to enable further vaccine development progress. The goal of this analysis is to provide highly valuable data of the novel Chikungunya vaccine for further development. Results from this analysis will have no impact on the study design and treatment of the subjects in this study.

All tables and listings marked with an "x" in column "IA" in section 10.1 and 10.1 will be generated for this Preliminary Analysis.

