The statistical analysis plan is based on the final study protocols for Austria (Version 1.5; 24-Nov-2016) and Germany (Version 1.6; 19-Apr-2017). No changes in the conduct of the planned analysis as described in the CSP are intended.

However, the time point of the Preliminary Analysis was moved forward to August 2017. The Preliminary Analysis was initially planned to take place after all subjects completed Visit 3.

Page 21 of 47

3. **OVERALL STUDY INFORMATION**

Treatment groups for the preliminary analysis as well the final analysis are defined in section 2.3. Overall study information analysis will be prepared for the:

- Preliminary analysis: mITT population. •
- Final analysis: Safety, mITT and PP population. •

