8.3 Adverse Events

Adverse Events are statistically analyzed once for the Preliminary Analysis up to Visit 3 and once for the final analysis.

The Preliminary Analysis includes all Adverse Events with a start date which is at of before the date of Visit 3. Adverse Events will be coded using the Medical Dictionary for Regulatory Activities (cp. section 2.15)

Solicited AEs comprise reactions at the injection site or systemic reactions that are typical for vaccinations:

- Solicited local AEs (injection site reactions) are the following: injection site pain, tenderness, pruritus, erythema (redness), edema, induration (hardening)
- Solicited systemic AEs are the following: headache, fever, myalgia, limb discomfort, arthralgia, flu-like symptoms, nausea, vomiting, rash and excessive fatigue.

For solicited local and systemic AEs were summarized for a 7 day period. Solicited AEs will not be coded into MedDRA and no assessment of relatedness was performed.

An AE is considered to be related to study drug if the "Causal relationship to study treatment" was considered "definite", "probable", "possible" or the classification is missing.

For solicited local and systemic AEs the following tables will be tabulated:

- at least one AE
- at least one serious AE
- at least one severe AE

SAP (MV-CHIK-202, FINAL 3.0, 09-May-2018) Page 32 of 47 Based on: STAT03_A Statistical Analysis Plan Version 5.0, Effective Date 16-Dec-2016 Confidential and intellectual property of Assign DMB. No part of this document or its contents may be duplicated, referenced, published or otherwise disclosed in any form or by any means without prior written consent of Assign DMB.

• at least one AE by severity

An AE is considered to be a treatment-emergent AE (TEAE) if, and only if, first onset or worsening is simultaneous with or after first vaccination (AE start date is greater or equal first vaccination date). AEs for which it cannot be clearly decided if the start date was before or on/after first vaccination will be considered treatment-emergent, following a worst case approach.

For unsolicited AEs the following tables will be tabulated:

- at least one TEAE
- at least one severe TEAE
- at least one serious TEAE
- at least one TEAE related to study drug
- at least one medically attended TEAE
- at least one TEAE where an action was taken (i.e. no action taken was NOT ticked)
- at least one TEAE of special interest (arthritis)

The same tables grouped by SOC and PT will be provided.

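### The final unsolicited adverse-event tables have no Day 56 cut, so the safety part of the primary objective gets unsolicited-event rates only from the earlier preliminary run

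*Protocol*

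**What the plan says.** Protocol 3.1, repeated in SAP 1.1.1, sets the primary objective: "To investigate the immunogenicity and safety of MV-CHIK 28 days after primary immunization regimen, comprising one or two vaccinations". Protocol 3.2 lists, as a separate secondary objective, safety over the whole treatment period to 28 days after the last treatment. The documents therefore name two safety windows.

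The primary endpoint in Protocol 4.1.1 is immunogenicity alone: "Immunogenicity on day 56 confirmed by the presence of functional anti-chikungunya antibodies". All safety endpoints stand in 4.1.2 as secondary, and Protocol 11.2 adds: "Adverse event rates will be used to evaluate the secondary study objective".

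SAP 8.3 fixes the analysis occasions: "Adverse Events are statistically analyzed once for the Preliminary Analysis up to Visit 3 and once for the final analysis". It gives a cut for the first only: "The Preliminary Analysis includes all Adverse Events with a start date which is at of before the date of Visit 3". A treatment-emergent event is any onset from first vaccination on, with no end date, and Protocol 13.2 has events recorded up to Visit 6 (Day 224). SAP 10.1 uses the same shells, Tables 4.2-4.11, in both runs. They are laid out by treatment group, or by system organ class, preferred term and group, with no visit or period.

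On the timing of the preliminary run, SAP 2.2.1 says: "The analysis was initially planned to be conducted after all subjects completed Visit 3 (Day 56) but was re-scheduled due to unforeseen delays". SAP 2.17 says: "However, the time point of the Preliminary Analysis was moved forward to August 2017". Under SAP 8 and 2.16 that run uses mITT, grouped as randomised. The Safety population, grouped by product received, is reserved for the final analysis.

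**The concern.** A primary objective should have a final analysis on complete data that answers it. For unsolicited, severe, serious, related, medically attended and special-interest events, the SAP offers two sets of tables. One has the right window but comes from a run brought forward from its planned trigger and grouped as randomised. The other has the right population but a window four times as long in groups A-D, including a further injection.

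At stake is the comparison that the objective names. At Day 56 groups A and C have had two active vaccinations and B and D one. That is the only point at which one-dose and two-dose safety can be set side by side, and the trial also aims to choose a dose and schedule for Phase 3. The Fisher tests in SAP 2.7.3, applied to the final tables, would address a different window.

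**Working it through.** The plan states no figure on this point, so there is none to reproduce. The check sets the schedule against the table layout.

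**1. Follow-up outside the primary window (unsolicited events).** Inputs: Day 56 (Protocol 4.1.1); recording to Day 224 (Protocol 13.2); first vaccination on Day 0 in A-D and Day -28 in M1/M2 (Protocol Table 1).

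- A-D: (224 - 56) / 224 = 168 / 224 = 75%.
- M1/M2: 168 / (224 + 28) = 168 / 252 = 67%.

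**2. Solicited events (Table 4.2).** These cover 7 days per injection.

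- A-D: injections on Days 0, 28 and 196, so one period of three (7 of 21 days, one third) falls after Day 56.
- M1/M2: Days 168 and 196 fall after Day 56, so two periods of five (14 of 35 days, 40%).

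The 75% figure therefore does not apply to Table 4.2.

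**3. Scheduled active injections (MV-CHIK, or control vaccine for the A-D controls; Protocol Table 1).** The initial measles vaccination in M1/M2 is not counted.

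| Group | By Day 56 | By Day 224 |
|---|---|---|
| A, C | 2 | 2 |
| B, D | 1 | 2 |
| M1 | 2 | 2 |
| M2 | 0 | 2 |

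In the final pooled tables A against B, and C against D, compare two doses at different intervals. No one-dose result remains. M2 has received no MV-CHIK by Day 56.

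**4. What the final run does give for the primary period, on the Safety population.** Solicited symptoms are tabulated by diary period (about Tables 4.29-4.44). Laboratory values, vital signs, symptom-directed examination and local tolerability are tabulated by visit. The gap is therefore Tables 4.3-4.11, plus the pooling in Table 4.2.

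**5. Illustration of dilution (assumed rates, not taken from the documents).** Let p be the control proportion with an event by Day 56 and d the MV-CHIK excess at that point. Assume the same constant background hazard in both arms afterwards. The 168 later days are three times 56, so the excess at Day 224 is d x (1 - p)^3.

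- p = 30%, d = 10 points: 10 x 0.70^3 = 10 x 0.343 = 3.4 points (76.0% against 79.4%).
- p = 15%, d = 10 points: 10 x 0.85^3 = 10 x 0.614 = 6.1 points.
- d = 20 points, p = 10%, 20%, 30%, 40%: 14.6, 10.2, 6.9 and 4.3 points. Fisher power for 60 against 20 falls from 0.40, 0.33, 0.31, 0.28 at Day 56 to 0.17, 0.10, 0.09, 0.08 at Day 224.

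Here 20 is the 10 + 10 controls sharing a schedule.

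**The case against.** The strongest reply is that the protocol treats safety as secondary and descriptive throughout. Every safety endpoint is in 4.1.2, Protocol 11.2 ties event rates to the secondary objective, and no hypothesis or decision rule rests on a Day 56 table. Final listings of unsolicited and serious events carry start dates, and the exposure listing carries first and last vaccination dates, so Day 56 counts could be derived. mITT and Safety both require at least one vaccination and differ essentially in as-randomised against as-treated grouping.

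Much of this stands, and it limits the point. It does not remove it: the objective still names safety at this window, a listing gives neither rates nor tests, and Protocol 13.2 asks for unsolicited events by product received.

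A reader might infer more than the documents support:

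- *That the safety half of the primary objective has no final output.* It has the diary-period and by-visit tables.
- *That the preliminary run is known to be missing many subjects.* The timing change implies that some had not reached Visit 3, but no count is given.
- *That the dilution figures estimate this trial.* They rest on assumed rates and on no vaccine effect after Day 56. That assumption fits A and C, whose Day 196 injection is saline, better than B and D, who receive active vaccine then. A-D also have no scheduled visit between Day 56 and Day 196 and no diary for most of that time, so later capture may be thinner and dilution smaller.
- *That Day 56 is the primary-regimen window for every group.* It is not for M2.

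**Conclusion.** The point holds for unsolicited events. If the SAP is followed as written, the final analysis gives no rate or test for them over the primary-objective window, and no one-dose MV-CHIK result. The only tables with that window come from a run brought forward from its planned trigger and grouped as randomised. The firm figures are the shares of unsolicited follow-up after Day 56: 75% in A-D and 67% in M1/M2. For Table 4.2 the issue is smaller: one 7-day period of three is pooled in from outside the window in A-D. The direction of dilution holds if background events accrue equally in both arms; its size cannot be taken from the documents. The conclusion assumes that Day 56 marks 28 days after the primary regimen in A-D and M1, and that the preliminary analysis was moved to an earlier date, as SAP 2.17 indicates. The change is worth making, but the primary immunogenicity result does not depend on it.

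**What to change.** - In SAP 8.3 and 10.1, repeat Tables 4.2-4.11 at the final analysis on the Safety population, for events with onset on or before Visit 3, or up to early termination if that came first. Name this the safety analysis of the primary objective.
- In that cut, show M2 separately and leave it out of the MV-CHIK total.
- Add a table of events with onset within 28 days after each vaccination. This serves the listed secondary endpoint on event rates in the four weeks after vaccination. In M1 it also separates the period after the initial measles vaccine from those after MV-CHIK.
- Keep the whole-study tables for the secondary objective, and amend Protocol 11.2 to refer to both objectives.

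The cost is SAP and protocol wording and additional tables. The Visit 3 cut is already specified and the table shells exist from the preliminary run; the 28-day table needs only an onset filter. No new data are required.
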